The adequacy of the linear assumption between ddQTcF and plasma concentrations will be determined by adding a quadratic term to the mixed-effects model. If the quadratic term is different than zero, having $P < 0.05$, and Akaike's information criterion (AIC) is smaller in comparison with the linear model's AIC, then a quadratic term may be added. In addition, a transformation of the concentrations (eg, $\log[C/LLOQ]$, where LLOQ is the lower limit of quantitation of the assay and all values below the LLOQ are replaced with the LLOQ) may also be assessed. The best model fit will be determined by the lowest AIC.

The predicted mean expected ddQTcF and the 90% 2-sided CI will be calculated using the estimates of the slopes from the mixed-effect models, for all subjects, at relevant concentration levels (ie, the mean maximum plasma concentration under each dose level).

The relevant SAS code statements are:

```
PROC MIXED DATA = DATA;  
  CLASS SUBJID;  
  MODEL ddQTcF = CONC /SOLUTION OUTPM=PRED ALPHA=0.05;  
  RANDOM INTERCEPT CONC / TYPE=UN SUBJECT = SUBJID;  
RUN;
```

In the above statements:

- CONC represents the measured plasma concentrations of moxidectin;
- Type=UN means an unstructured covariance matrix, which is used for the correlated random effects (INTERCEPT and CONC). If the model does not converge other covariance structures will be investigated.

A plot will be provided to show CI of each treatment using the following model, adding in the treatment variable as follows:

```
PROC MIXED DATA = DATA;  
  CLASS SUBJID TRT;  
  MODEL ddQTcF = CONC TRT/SOLUTION OUTP=PRED;  
  RANDOM INTERCEPT CONC /TYPE=UN SUBJECT = SUBJID;  
RUN;
```

Where TRT represents the individual treatments (moxidectin 4 mg, moxidectin 8 mg, moxidectin 16 mg, moxidectin 24 mg, and moxidectin 36 mg).

A plot of the observed median-decile drug concentrations and associated mean ddQTcF (90% CI) together with the mean model-predicted ddQTcF will be used to evaluate the adequacy of the model fit to the assumption of linearity and the impact on quantifying the concentration response relationship.

Categorical QTc Findings

Categorical summaries using the largest postdose QTcF and largest change from Baseline (dQTcF) will be performed to determine the number and percentage of subjects, by treatment, who meet each of the following criteria:

- Result ≤ 450 msec;
- Result > 450 and ≤ 480 msec;
- Result > 480 and ≤ 500 msec;
- Result > 500 msec;
- dQTcF ≤ 30 msec;

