14.2 Pharmacokinetic and Pharmacodynamic Summary Tables

14.2.1 Concentration and Pharmacokinetic Summaries, Analyses, and Figures

Table 14.2.1.1	Summary of Plasma Concentrations Over Time (PK Population)
Table 14.2.1.2	Summary of Plasma Pharmacokinetic Parameters (PK Population)
Table 14.2.1.3	Summary of Urine Pharmacokinetic Parameters (PK Population)
Table 14.2.1.4	Summary of Feces Pharmacokinetic Parameters (PK Population)
Figure 14.2.1.1	Mean \pm SD Plasma Moxidectin Concentration (ng/mL)-Time Profile, Linear Scale (PK Population)
Figure 14.2.1.2	Mean Plasma Moxidectin Concentration (ng/mL)-Time Profile, Semilogarithmic Scale (PK Population)
Figure 14.2.1.3	Mean \pm SD Plasma Moxidectin Metabolite Concentration (ng/mL)-Time Profile, Linear Scale (PK Population)
Figure 14.2.1.4	Mean Plasma Moxidectin Metabolite Concentration (ng/mL)-Time Profile, Semilogarithmic Scale (PK Population)
Figure 14.2.1.5	Mean \pm SD Plasma Moxidectin Metabolite to Parent (molar equivalents) Ratios Over Time (PK Population)
Figure 14.2.1.6	Mean \pm SD Urine Moxidectin Amount Excreted Over Time (PK Population)
Figure 14.2.1.7	Mean \pm SD Urine Moxidectin Metabolite Amount Excreted Over Time (PK Population)
Figure 14.2.1.8	Mean \pm SD Urine Moxidectin Metabolite to Parent Amount Excreted (molar equivalents) Ratios Over Time (PK Population)
Figure 14.2.1.9	Mean \pm SD Feces Moxidectin Amount Excreted Over Time (PK Population)

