14.2.2 Pharmacodynamic Summaries, Analyses, and Figures

Table 14.2.2.1	Summary of Continuous ECG Parameter Results and Change From Baseline (ECG Population)
Table 14.2.2.2	Summary of Simple/Unadjusted Continuous ECG Parameters (ECG Population)
Table 14.2.2.3	Summary of Primary Analysis Mixed-Effects Model Parameters (ECG Population)

Table 14.2.2.4	Summary of Primary Analysis Mixed-Effects Model Predicted ddECG and Predicted Interval at Geometric Mean Maximum Plasma Concentration (ECG Population)
Table 14.2.2.5	Summary of Secondary Analyses Mixed-Effects Model Predicted Regression Slope Estimates and Predictions (PK/PD Population)
Table 14.2.2.6	Summary of Continuous QTcF Interval Categories (ECG Population)
Table 14.2.2.7	Summary of Continuous PR, QRS, and HR Outliers (ECG Population)
Table 14.2.2.8	Summary of Continuous ECG Diagnostic Statements (ECG Population)
Table 14.2.2.9	Summary of Treatment-Emergent Continuous ECG Diagnostic Statements (ECG Population)
Figure 14.2.2.1	dQTcF Interval vs. Time Showing Mean and 2-sided 90% Confidence Bounds (ECG Population)
Figure 14.2.2.2	dHR vs. Time Showing Mean and 2-sided 95% Confidence Bounds (ECG Population)
Figure 14.2.2.3	dPR Interval vs. Time Showing Mean and 2-sided 95% Confidence Bounds (ECG Population)
Figure 14.2.2.4	dQRS Interval vs. Time Showing Mean and 2-sided 95% Confidence Bounds (ECG Population)
Figure 14.2.2.5	dRR Interval vs. Time Showing Mean and 2-sided 95% Confidence Bounds (ECG Population)
Figure 14.2.2.6	ddQTcF Interval vs. Time Showing Mean and 2-sided 90% Confidence Bounds (ECG Population)
Figure 14.2.2.7	ddHR vs. Time Showing Mean and 2-sided 95% Confidence Bounds (ECG Population)
Figure 14.2.2.8	ddPR Interval vs. Time Showing Mean and 2-sided 95% Confidence Bounds (ECG Population)
Figure 14.2.2.9	ddQRS Interval vs. Time Showing Mean and 2-sided 95% Confidence Bounds (ECG Population)
Figure 14.2.2.10	ddRR Interval vs. Time Showing Mean and 2-sided 95% Confidence Bounds (ECG Population)
Figure 14.2.2.11	Residual Plots From Primary Analyses by Parameter (ECG Population)
Figure 14.2.2.12	ddQTcF Interval vs. Plasma Moxidectin Concentrations (PK/PD Population)
Figure 14.2.2.13	ddQTcF Interval vs. Plasma Moxidectin Concentration by Treatment (PK/PD Population)
Figure 14.2.2.14	Observed Median-decile Plasma Moxidectin Concentrations and Associated Mean ddQTcF Interval (90% CI) Together With the Mean (90% CI) Predicted ddQTcF Interval (PK/PD Population)

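### Secondary ddQTcF models with different fixed effects are ranked by AIC, but the printed code fits by REML, so the ranking depends on the concentration unit

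*SAP*

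**What the plan says.** The secondary analysis in SAP section 8.3 regresses ddQTcF on time-matched moxidectin concentration in a mixed model with random intercept and slope. Linearity is checked by adding a quadratic term. If that term has P < 0.05 and the AIC "is smaller in comparison with the linear model's AIC, then a quadratic term may be added". A transformation such as log[C/LLOQ] is also allowed: "all values below the LLOQ are replaced with the LLOQ) may also be assessed". The closing rule is "The best model fit will be determined by the lowest AIC".

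The model statement printed for this analysis is "MODEL ddQTcF = CONC /SOLUTION OUTPM=PRED ALPHA=0.05". Its PROC MIXED line names only the data set. No section of the SAP mentions ML, REML or a separate fit for model comparison.

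The model feeds a reported result: "The predicted mean expected ddQTcF and the 90% 2-sided CI will be calculated using the estimates of the slopes from the mixed-effect models", at levels such as the mean maximum concentration of each dose. Appendix A lists the output as Table 14.2.2.5, "Summary of Secondary Analyses Mixed-Effects Model Predicted Regression Slope Estimates and Predictions (PK/PD Population". The concentration unit appears in the PK figure titles, for example "Mean Plasma Moxidectin Concentration (ng/mL)-Time Profile, Semilogarithmic Scale (PK Population".

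**The concern.** PROC MIXED uses REML unless told otherwise. The REML likelihood measures fit after the fixed effects have been projected out, so its value depends on which fixed-effect columns are in the model and on their units. Its AIC is suitable for comparing covariance structures with the same fixed effects. It is not suitable for comparing C, C plus C², and log[C/LLOQ].

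Two errors can follow when C is in ng/mL:

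- The quadratic model carries an arbitrary handicap against the linear one. The joint condition of P < 0.05 and a smaller AIC is then much stricter than P < 0.05 alone, and real curvature can be turned down.
- The linear model carries a similar handicap against the log model. A log curve can be chosen when the relation is linear, and it then under-predicts ddQTcF at the highest Cmax. No P-value condition guards this choice.

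The secondary model is also the SAP's own safeguard. Section 8.3 justifies it by the risk that circadian change makes the primary dQTcF slope spurious. A safeguard should not depend on the unit in which concentration is stored.

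**Working it through.** **Inputs from the SAP.** The candidates, the AIC rule and the code are in section 8.3, and the ng/mL unit is in Appendix A. The SAP gives no figure for this comparison. Its one design count, 900 pairs, is reproduced as 60 subjects × 15 extraction times (baseline plus 14 postdose). The active postdose data number 50 × 14 = 700.

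**Exact part, no assumptions.** The REML objective is

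−2ℓ_R = log|V| + log|X′V⁻¹X| + r′V⁻¹r + (n − p) log 2π,

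and AIC = −2ℓ_R + 2 × (number of covariance parameters). Multiply C by k. The random slope rescales with it, so V and the residuals r are unchanged. Only log|X′V⁻¹X| moves:

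- linear (columns 1, C): + 2 ln k
- quadratic (columns 1, C, C²): + 2 ln k + 4 ln k = 6 ln k
- log[C/LLOQ]: 0

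From ng/mL to µg/mL, k = 0.001 and ln k = −6.908. Hence:

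- quadratic minus linear shifts by 4 × (−6.908) = −27.6
- linear minus log shifts by 2 × (−6.908) = −13.8

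The ML objective has no such term, so both shifts are 0. Direct refits gave 27.631 and 13.816.

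**One simulated data set with a linear truth** (assumed concentrations, residual SD 6 msec, between-subject SD 4 msec):

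| AIC | linear | quadratic | log | lowest |
|---|---|---|---|---|
| REML, ng/mL | 4608.17 | 4625.90 | 4601.59 | log |
| REML, µg/mL | 4594.35 | 4584.46 | 4601.59 | quadratic |
| ML, either unit | 4604.21 | 4605.98 | 4605.07 | linear |

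Under ML the quadratic term gains only 2 − (4605.98 − 4604.21) = 0.23 in likelihood-ratio chi-square, which is no evidence of curvature. REML in µg/mL still ranks the quadratic first by 9.9; the P < 0.05 condition would stop its adoption at the quadratic step. REML in ng/mL ranks it 17.7 behind the linear model, so a chi-square of about 17.7 + 0.2 ≈ 18 would be needed to overturn that, against 3.84 for P < 0.05.

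**How often it matters (assumption-dependent).** The design was 50 active subjects × 14 times with 250 data sets per truth. Assumed were a 36-mg Cmax of 50–500 ng/mL, dose proportionality, 30% between-subject CV, a biphasic profile and LLOQ = Cmax/2000. Residual SD was 7, intercept SD 6 and slope SD 3 msec at Cmax. With x = C/Cmax, the truths were 10x², 15x − 10x², −4x + 14x², 8x and 4x.

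- *Quadratic against linear, ng/mL.* The chi-square needed is about 11–21. Where P < 0.05 has 84–85% power, the printed rule adopts the quadratic in 7–37% of data sets, against 84–85% with ML AIC. At 98% power it adopts it in 30–72%, against 98%. Keeping the linear model misses the value at the 36-mg mean Cmax by −2.1 msec (convex), +2.0 (concave) or −3.4 (stronger convex).
- *Log against linear, truth 8x.* REML picks log in 32%, 43%, 55% and 60% at Cmax 50, 100, 300 and 500, against 8% with ML. The log model then under-predicts by 3.0 msec on average. With truth 4x it is 84–94% against 26%, and 1.5 msec.
- *All three candidates, truth 8x.* The upper limit of the 90% interval falls below the true value in 27–45% of data sets, against 12% with ML.
- *Other variances (120 data sets each).* Residual, intercept and slope SDs of 5/5/1.5 give quadratic adoption of 29–71% against 98%, and false log choice of 8–20% against 4%. SDs of 10/8/5 give 2–12% against 63%, and 56–78% against 19%.

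A separately coded simulation, also on assumed inputs, agreed in direction: a true quadratic was adopted in 13–42% under REML against 87–88% under ML, and log was preferred to a true linear model in 20–30% against 8%.

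**The case against.** The strongest reply is that the SAP is silent on the estimation method for the comparison and does not prescribe REML for it. Code is printed only for the linear model and for a by-treatment plot model, REML is proper for the estimates those produce, and SAP section 4 asks for procedures suited to each analysis. A careful programmer could use ML. That is possible, but the only code given runs under REML and the deciding sentence names AIC without qualification. Following the text as written gives an invalid ranking.

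Second, the ng/mL unit is inferred from PK figure titles, since section 8.3 defines the concentration variable without a unit. This is true, and it limits the simulated percentages. It does not help the rule, because a ranking that changes with an unstated unit is itself the defect.

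Third, the quadratic and log steps are worded as options, and the quadratic P-value remains valid under REML, so significant curvature would be visible. Residual and median-decile plots are also planned. These points soften the harm. They do not change which model the lowest-AIC sentence selects, and the SAP gives the plots no rule that overrides it.

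Fourth, part of the error is ordinary selection error. Even under ML the upper limit misses in 12% of data sets, against a nominal 5%. That part stands and the fix will not remove it.

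Finally, no pass/fail threshold rests on this analysis: the 10-msec criterion belongs to the primary dQTcF model. That also stands and limits the weight of the point.

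**Conclusion.** The concern holds. Applied with the printed code, the lowest-AIC rule compares quantities that are not comparable, and its ranking moves with the concentration unit. The shifts of 27.6 and 13.8 between ng/mL and µg/mL are exact. The selection rates and errors of roughly 1.5 to 3.4 msec are illustrative: they rest on assumed Cmax, LLOQ, PK shape and variances, and the rates varied widely between settings, though REML did worse than ML in each. The log results apply only if that optional model is fitted.

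The effect is confined to the secondary predicted ddQTcF and its 90% interval at each dose's mean Cmax. The primary conclusion is not directly affected. The rule should be corrected before unblinding, since section 4 treats these as a priori analyses.

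**What to change.** Add one sentence to the secondary analysis in SAP section 8.3: all AIC comparisons among the linear, quadratic and log[C/LLOQ] models use `METHOD=ML`, on the same observations and with the same type of random-effects structure, and the selected model is then refitted by REML for the estimates and 90% intervals. Show `METHOD=ML` in the PROC MIXED statement used for the comparison. The cost is one code option and one sentence, with no change to data collection or sample size.

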2.4.2 Pharmacodynamic Endpoints

The PD endpoints are calculated from the mean of the triplicate continuous 12-lead ECG data as:

1. $dQTcF$ – baseline-adjusted QT interval corrected by Fridericia's formula ($QTcF$);
2. $ddQTcF$ – time-matched, placebo-corrected, baseline-adjusted $QTcF$, which is calculated as the $dQTcF$ minus the time-matched mean $dQTcF$ of all placebo subjects at each postdose time point ($ddQTcF=[dQTcF(\text{active dose groups})-\text{mean } dQTcF(\text{placebo})]$);

The primary study endpoint is the $dQTcF$ matched to the plasma concentration of moxidectin collected at the same time point.

Analogous-derived exploratory endpoints are also calculated for heart rate (HR), and duration of PR, RR, and QRS interval parameters.

The ECG morphologic changes data are also considered an exploratory endpoint.

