3.3 Study Design

This is a randomized, single-center, double-blind, placebo-controlled, parallel-group study in which healthy male subjects will be randomly assigned to one of the following treatments:

- Treatment 1: moxidectin 4 mg (n = 10)
- Treatment 2: moxidectin 8 mg (n = 10)
- Treatment 3: moxidectin 16 mg (n = 10)
- Treatment 4: moxidectin 24 mg (n = 10)
- Treatment 5: moxidectin 36 mg (n = 10)
- Treatment 6: matching placebo (n = 10)

Subjects will be screened for eligibility up to 28 days before randomization. Subjects who meet all of the inclusion and none of the exclusion criteria will be admitted to the CRU on Day -1 (not less than 12 hours before scheduled dosing). Subjects will remain in the CRU for at least 72 hours after dosing and will return to the CRU for further assessment on Days 8, 15, and 22, and Week 12. At Week 8, subjects will be contacted via telephone for recording of AEs and concomitant medication use.

Randomized subjects will be assigned unique subject numbers in sequential order based on their order of qualification. Randomization will take place before dosing on Day 1, with equal random assignment to each treatment. Subjects are considered as enrolled once randomized.

The duration of participation in the study for each subject will be up to approximately 112 days, including Screening.

For purposes of statistical analysis, this study is divided into 2 study periods:

- Period 1: Commences at Screening and will finish on Day 22. The study blind will be maintained during this study period. After the last subject has completed the study through Period 1, the blind will be broken and the data from Period 1 will be analyzed.
- Period 2: Runs from Day 23 to Week 12. Data from Period 2 will be analyzed after all subjects have completed the study through Week 12. Data for some subjects may be collected during Period 2 after the blind has been broken.

The overall schedule of events is provided in Table 1 and the Period 1, Day -1 to Day 4 schedule of events is provided in Table 2.

Table 1. Overall Schedule of Events

Assessment	Screening D-28 to D-2	Period 1									Period 2										
		D-1	Baseline D1 (Predose)	D1	D2	D3	D4	D8	D15	D22	W8	W12 ^f									
Outpatient visit	X	Refer to Table 2: Schedule of Events for Period 1 (Day -1 to Day 4)									X	X	X		X						
Informed consent	X																				
Telephone call																				X	
Inclusion/exclusion criteria review	X																				

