5.4 Pharmacokinetic/Pharmacodynamic Population

The PK/PD population will include all subjects in the ECG population who have time-matched plasma concentrations for the active moxidectin treatments. Subjects in this population will be analyzed according to the drug received (actual drug concentration).

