8.2 General Summaries

All continuous 12-lead ECG data collected will be presented in data listings. Data from subjects excluded from the analysis populations will be presented in the data listings, but not included in the calculation of summary statistics. For categorical variables, frequencies and percentages will be presented. Continuous variables will be summarized using descriptive statistics (n, mean, SD, 2-sided confidence bounds [90% for the QTcF interval or 95% for other parameters], median, 25th percentile, 75th percentile, minimum, and maximum). The mean of the triplicate 0-hour time point on Day 1 will be used as the

baseline. The continuous 12-lead ECG parameters (QTcF, HR, PR, RR, and QRS) and the corresponding changes from Baseline (denoted as dQTcF, dHR, dPR, dRR, and dQRS) and placebo-adjusted endpoints (denoted as ddQTcF, ddHR, ddPR, ddRR, and ddQRS) will be summarized by treatment and time point.

The means and 90% CIs for the dQTcF and placebo-adjusted (algebraic) ddQTcF will be calculated across all subjects for each time point and each active treatment and displayed graphically. Secondary endpoints will also be displayed using 95% CI, if applicable.

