8.3 Statistical Analyses

Primary Analysis

The relationship between time-matched, baseline-adjusted QTcF (dQTcF) and moxidectin concentrations will be investigated by linear mixed-effects modeling. The ddQTcF value will be calculated as the placebo-corrected dQTcF estimated from the model.

Before modeling, the concentration-ddQTcF relationship will be explored graphically to determine the presence of hysteresis. Hysteresis will be assumed if, on average (or median), there are at least 3 time points with ddQTcF >5 msec and the time to maximum observed plasma concentration (T_{max}) and the time of maximal ddQTcF (U_{max}) differ by 30 minutes or more and the 1-sided, 1-sample Wilcoxon test for the difference between ddQTcF at T_{max} and at U_{max} is significant at the 1% level. If hysteresis is present, the possibility of fitting a population PK model with an effect compartment will be explored.

The primary analysis will be provided for the ECG population using a mixed-effects model with dQTcF as the dependent variable and treatment (active and placebo), time point, and treatment by time point interaction as the independent variables with baseline QTcF as a covariate and time-matched concentrations of moxidectin (observed if hysteresis is not present; predicted from the effect compartment if hysteresis is present) as a covariate with random effects of intercept and slope. Concentrations of zero will be used for the placebo treatment. A spatial power law covariance structure (a time-dependent first-order autoregressive covariance designed for unequally-spaced time points) will be used. If the model does not converge then unstructured (UN) or compound symmetry (CS) structures will be assessed, in that order. The model will be used for predicting population average and 90% 2-sided bootstrapped CI of the baseline-adjusted difference (ie, ddQTcF) between active and placebo at each time point bound at clinically relevant concentrations. The bootstrap method will be based on percentile CI using the 5th and 95th percentiles in the resampling distribution using 1000 iterations.

The criterion for negative QT assessment will be the upper bound of the 2-sided 90% bootstrapped CI for ddQTcF being below 10 msec at the largest geometric mean C_{max} value. In addition, the significance and magnitude of parameter estimates of the treatment covariate (active vs. placebo) will be considered.

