  LSMEANS TRT TRT*ATPTN /DIFF ALPHA=0.1 CL;  
RUN;
```

In the above statements:

- TRT represents the treatment (active or placebo);
- ATPTN represents the postdose nominal time point;
- BASE represents the baseline value for QTcF;
- CONC represents measured plasma concentrations of moxidectin;

- SP(POW) is a spatial power law covariance structure (a time-dependent first-order autoregressive covariance designed for unequally-spaced time points), if the model does not converge then unstructured or compound symmetry structures will be assessed, in that order;
- LSMEAN differences between the treatments at the Geometric C_{\max} value and at the average concentration value, where xx.x represents the largest geometric mean C_{\max} value among the doses, most likely for the 36-mg dose, will be provided.

Model assumptions will be reviewed with plots of standardized residuals versus fitted values and normal Q-Q plots of the standardized residuals. If nonlinearity is present, a log linear and/or maximum effect (E_{\max}) or other model will be considered.

Similar analyses will be repeated for HR, PR, and QRS, however, bootstrap percentiles will be based on the 2.5th and 97.5th percentiles, corresponding to a 2-sided 95% CI rather than the 2-sided 90% CI.

Secondary Analysis: Pharmacokinetic/Pharmacodynamic Analyses

To evaluate the relationship between placebo-corrected mean change from Baseline in QTcF (ie, ddQTcF) versus plasma concentrations of moxidectin for all subjects in the PK/PD population, both graphical and mixed-effects analyses of plasma concentration of ddQTcF versus plasma concentration of moxidectin will be performed. The mixed-effects model will be used to account for the clustering effects within each subject at different time points. The mixed-effects model will contain ddQTcF as the dependent variable and include the corresponding time-matched plasma moxidectin concentrations as the independent variable. The mixed-effects model will be used to estimate, for all subjects, the predicted population mean ddQTcF and its corresponding upper 95% 1-sided (equivalent to the upper 90% 2-sided) CI over a range of observed plasma concentrations. A negative result (ie, the model indicates no plasma concentration effect) is a slope of approximately zero.

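### The secondary concentration-ddQTcF model treats the mean of 10 placebo subjects as known, so its 90% intervals at each dose's Cmax are too narrow; the by-time-point ddQTcF intervals share the fault to a moderate degree

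*SAP*

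**What the plan says.** SAP 2.4.2 defines ddQTcF as a subject's dQTcF minus the time-matched mean dQTcF "of all placebo subjects at each postdose time point". The placebo arm has 10 subjects and the five active arms have 10 each (SAP 3.3).

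The secondary analysis in SAP 8.3 uses the PK/PD population, which SAP 5.4 limits to ECG-population subjects with "time-matched plasma concentrations for the active moxidectin treatments". "The mixed-effects model will contain ddQTcF as the dependent variable", and time-matched concentration is the only independent variable. The code is "MODEL ddQTcF = CONC /SOLUTION OUTPM=PRED ALPHA=0.05", with a random intercept and slope by subject. It has no placebo records, no time term and no bootstrap. From this model the SAP takes an upper limit over the observed concentrations and an interval at each dose's mean Cmax: "The predicted mean expected ddQTcF and the 90% 2-sided CI will be calculated using the estimates of the slopes from the mixed-effect models".

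SAP 8.2 also asks for intervals by time point: means and 90% CIs for dQTcF and "placebo-adjusted (algebraic) ddQTcF will be calculated across all subjects for each time point and each active treatment". It lists the confidence bounds beside n, mean and SD as descriptive statistics and gives no formula.

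The primary model in SAP 8.3 differs. Its outcome is dQTcF, placebo subjects are in it, and "Concentrations of zero will be used for the placebo treatment".

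**The concern.** Subtracting an estimated placebo mean adds that mean's sampling error to every active subject's value. The error is the same for all active subjects at a time point, so it does not average out as active subjects are added. A model that takes subjects as independent cannot see it, and its standard error reflects only variation among the active subjects.

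SAP 8.3 wants this analysis because a dQTcF slope could be distorted by circadian change. Its upper limits, its per-dose intervals at Cmax and the by-time ddQTcF figure (Figure 14.2.2.6) will therefore be read alongside the primary result. If they are too narrow, the supportive evidence looks firmer than the data allow. The SAP reads a slope near zero as a negative result, and the precision of that slope is overstated as well.

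**Working it through.** **The plan's own figure.** SAP 3.2 states 900 QTc-PK pairs: 60 subjects × 15 time points (baseline plus 14 postdose) = 900. This reproduces, but it counts baseline and placebo. The secondary model can use at most 50 × 14 = 700 pairs. The SAP gives no SD, power or interval width.

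**Limiting case.** Let the error be a persistent subject-level deviation with variance σ² in both arms.

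- Variance seen by the model: σ²/50.
- True variance: σ²/50 + σ²/10.
- Ratio of standard errors: √[(1/50 + 1/10)/(1/50)] = √(0.12/0.02) = √6 = 2.45, whatever σ is.
- Coverage of a nominal 90% normal interval: P(|Z| < 1.645/2.45) = P(|Z| < 0.67), about 50%.

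**Simulation of the secondary model.** These inputs are assumptions, because the SAP gives none:

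- subject-level and residual SDs of (5, 5), (5, 8) or (8, 8) msec;
- residual correlation 0 or 0.8 per hour;
- between-subject slope SD 0 or 6 msec at the 36-mg Cmax;
- dose-proportional Cmax with about 30% CV and Tmax 3–4 h;
- concentrations at 24 h and 72 h of 42% and 31% of Cmax, or 17% and 10%.

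That makes 3 × 2 × 2 × 2 = 24 settings. Each had 2,000 trials with true effect zero, a REML fit with random intercept and slope (unstructured covariance), and t limits on 49 df. The Monte Carlo SE is about 1.1 points on coverage.

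| At mean Cmax of | True SD / model SE | Coverage of 90% CI | Upper limit below truth (nominal 5%) |
|---|---|---|---|
| 4 mg | 2.3–2.4 | 51–53% | 24–26% |
| 16 mg | 2.2–2.4 | 51–57% | 22–26% |
| 36 mg | 1.8–2.5 | 52–65% | 17–24% |

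Example: with both SDs 5 msec and uncorrelated residuals, the model half-width at the 36-mg Cmax is 1.7 msec and about 3.7 msec is needed.

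**Independent check.** An exact generalised least squares variance was computed with other assumptions: subject SD 3–8, residual SD 6–8, correlation 0 or 0.9 per hour, slope SD 0 or 5 msec per 36-mg Cmax, and 35% CV. The factor was 2.05–2.45 at the 4- to 16-mg Cmax (coverage 50–58%) and 1.7–2.3 at 36 mg (52–66%). The slope's own standard error was too small by 1.7–2.0.

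**Control.** In 250 trials in each of three settings, the ratio was 0.94–1.08 without the placebo-mean error and 2.2–2.4 with it. The shortfall therefore comes from that error.

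**By time point**, read as one-sample intervals with n = 10 per arm and equal SDs:

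- Subtracting a constant leaves the SD unchanged, so the reported SE is s/√10. The true variance is σ²(1/10 + 1/10), and the standardised mean is distributed as √2 × t(9).
- 90% interval: coverage is P(|t(9)| < 1.833/√2) = 77.3%, and the upper limit misses 11.4% of the time. The half-width should be 1.734 × 1.414/1.833 = 1.34 times as wide.
- 95% intervals (ddHR, ddPR, ddRR, ddQRS): coverage is P(|t(9)| < 2.262/√2) = 85.6%. The factor is 2.101 × 1.414/2.262 = 1.31.

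**The case against.** - **The by-time-point part is a reading.** SAP 8.2 writes no formula, and a two-sample interval would be compatible with its text. This stands in part. However, the bounds are listed with n, mean and SD as descriptive statistics of the placebo-adjusted value for each treatment, and that describes a one-sample interval.
- **The primary model already gives valid ddQTcF intervals.** It does, at clinically relevant concentrations including the largest geometric mean Cmax, and with placebo in the model. The remaining gap is smaller for that reason. But treatment there is pooled active against placebo, and the Cmax values of the lower doses are not listed. The secondary and by-time intervals will still be reported as they come out.
- **The analysis is only supportive.** Agreed. No numeric threshold is attached to it, and the SAP calls the method typical. Common use does not restore coverage when one 10-subject mean serves 50 subjects.
- **The code does not produce the interval assessed.** `ALPHA=0.05` gives 95% limits where the text asks for 90%. This is a separate inconsistency and no rescue: the 95% limits covered only 59–65% in simulation.
- **The text speaks of slopes only.** If the intercept were left out, the per-dose figures above would not apply directly, but the slope's standard error is still too small by 1.7–2.0.
- **The sizes rest on assumed SDs and PK.** True. The direction does not.

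**Conclusion.** The concern holds. For the secondary model it follows directly from the definition of ddQTcF, the population and the code. Across the assumed ranges in the two main calculations, the true standard error at the dose Cmax is 1.7 to 2.5 times the reported one, and nominal 90% intervals cover about 50% to 66%. The exact size depends on SDs and a concentration profile that the SAP does not give, and on equal variances in active and placebo.

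For the by-time-point intervals the fault is moderate (77.3% coverage for 90%, 85.6% for 95%) and depends on the one-sample reading.

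The primary negative-QT criterion, the point estimates and their circadian correction are not affected. This should be fixed, because it misstates the precision of supportive results, but it does not threaten the primary decision.

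**What to change.** 1. **By time point (SAP 8.2).** State that each ddQTcF, ddHR, ddPR, ddRR and ddQRS interval is the two-sample interval for the difference in change from Baseline between that dose and placebo. It can be a Welch interval, or LSMEANS from a dose-by-time model that includes placebo.
2. **Secondary model (SAP 8.3).** Resample whole subjects within each active dose group and within placebo. In each resample, recompute the placebo means and ddQTcF and refit the model. Report percentile 90% limits at each dose's mean Cmax and over the concentration range.
3. **State the remaining shortfall.** In one check (both SDs 5 msec, uncorrelated residuals, slope SD 0, slower profile; 300 trials × 200 resamples) the bootstrap gave 85% coverage at the 36-mg Cmax, 7% upper misses and a half-width of 3.5 msec. With only 10 placebo subjects it does not fully reach 90%, and the report should say so. Taking the per-dose intervals from a dQTcF model that includes placebo is an alternative that was not simulated here.
4. **Align the code** with the 90% level in the text.

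The cost is SAP wording and modest programming, with data already collected and a bootstrap already planned for the primary analysis. The reported secondary and descriptive intervals will be wider.
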